14 PHARMACEUTICAL INFORMATION

14.1 BINTRAFUSP ALFA (M7824, MSB0011359C) (IND # 154950)

14.1.1 Source/Acquisition and Accountability

Bintrafusp alfa is manufactured and supplied for the trial by EMD Serono Research and Development Institute.

14.1.2 Toxicity

Most of the observed AEs with bintrafusp alfa are similar with class effects of monoclonal antibody blockade of the anti-PD-1/PD-L1 axis, with additional cutaneous side effects presumed to be related to TGF- β signaling modulation. The safety data summarized from April 2020 include data on the pooled expansion cohorts (630 participants): treatment-related (TR) treatment-emergent adverse events (TEAEs) were reported in 426 (67.6%) participants. (47) Most TR

TEAEs were low grade (Grade 1 or 2), while Grade ≥ 3 TR TEAEs occurred in 142 participants (22.5%), and immune related adverse events (irAEs) occurred in 137 (21.7%) participants.

Treatment-related TEAE Leading to Permanent Treatment Discontinuation by System Organ Class and Preferred Term in ≥ 2 participants in the Pooled Analysis of Dose Expansion Cohorts

System Organ Class (SOC) Preferred Term (PT)	EMR200647-001 N = 539 n (%)	MS200647-0008 N = 91 n (%)	Overall N = 630 n (%)
Related TEAE leading to permanent treatment discontinuation	38 (7.1)	12 (13.2)	50 (7.9)
Skin and subcutaneous tissue disorders	11 (2.0)	2 (2.2)	13 (2.1)
Rash maculo-papular	3 (0.6)	1 (1.1)	4 (0.6)
Eczema	1 (0.2)	1 (1.1)	2 (0.3)
Rash	2 (0.4)	0	2 (0.3)
Investigations	6 (1.1)	3 (3.3)	9 (1.4)
Alanine aminotransferase increased	3 (0.6)	1 (1.1)	4 (0.6)
Lipase increased	2 (0.4)	1 (1.1)	3 (0.5)
Aspartate aminotransferase increased	1 (0.2)	1 (1.1)	2 (0.3)
Gamma-glutamyltransferase increased	1 (0.2)	1 (1.1)	2 (0.3)
Gastrointestinal disorders	7 (1.3)	0	7 (1.1)
Colitis	3 (0.6)	0	3 (0.5)
Respiratory, thoracic and mediastinal disorders	5 (0.9)	1 (1.1)	6 (1.0)
Pneumonitis	3 (0.6)	0	3 (0.5)
Dyspnoea	2 (0.4)	0	2 (0.3)
Blood and lymphatic system disorders	4 (0.7)	1 (1.1)	5 (0.8)
Anaemia	1 (0.2)	1 (1.1)	2 (0.3)
Eosinophilia	2 (0.4)	0	2 (0.3)
Renal and urinary disorders	3 (0.6)	0	3 (0.5)
Acute kidney injury	3 (0.6)	0	3 (0.5)
Endocrine disorders	2 (0.4)	0	2 (0.3)
Adrenal insufficiency	2 (0.4)	0	2 (0.3)

Source: ADAE 30OCT2018 12:04 Outputid: t31.doc.

TEAEs leading to death occurred in 79 (12.5%) participants with similar rates in EMR200647-001 and MS200647-0008; 7 deaths were due to treatment-related TEAE: 1 participant had dyspnea, hemolysis and thrombocytopenia, 1 participant had an intracranial tumor hemorrhage, 1 participant had pneumonia, 2 participants died of interstitial lung disease, 1 participant due to sudden death, and 1 due to septic shock.

Common TEAEs (occurring in more than 10% of participants) were:

- Anemia (29%)
- Decreased appetite (25%)

- Fatigue (tiredness) (22%)
- Pruritus (itching) (21%)
- Dyspnea (shortness of breath) (21%)
- Constipation (19%)
- Nausea (19%)
- Pyrexia (fever) (19%)
- Asthenia (weakness, fatigue) (17%)
- Diarrhea (16%)
- Abdominal pain (15%)
- Vomiting (14%)
- Cough (13%)
- Headache (12%)
- Epistaxis (12%)
- Rash (11%)
- Elevation of aspartate aminotransferase (AST, liver enzyme) (11%)
- Leg or arm swelling (10%)

Skin-related adverse events which were possibly due to TGF- β inhibition, occurred in 11% of participants and included keratoacanthomas (7%), squamous cell carcinoma of the skin (3%), and hyperkeratosis (1%) and are important identified risks with bintrafusp alfa.

Anemia, alterations in wound healing or repair of tissue damage, and embryofetal toxicity remain important potential risks.

At least 2 instances of nodular regenerative hyperplasia have been observed with the use of this agent.

In addition, mucosal bleeding events (e.g. gum bleeding, nose bleeds, coughing up blood, blood in urine or stool) are a potential risk for bintrafusp alfa, included in the informed consent document.

Infusion-related Reactions (including reactions, signs and symptoms) occurred in 38 (6%) participants in the pooled safety analysis, and all IRRs were of Grade 1 or 2 intensity; most of the IRRs had an onset after the first or second infusion; those with onset after the third infusion (or later) were less frequent. Consequently, the administration of premedication is not required. As per Section 3.2.3, if an Investigator deems necessary to administer a premedication to a particular participant, an antihistamine (e.g. 25 to 50 mg diphenhydramine) and paracetamol (acetaminophen, 500 to 650 mg intravenously or equivalent oral dose) 30 to 60 minutes prior to bintrafusp alfa infusion is recommended. Premedication should be administered for subsequent bintrafusp alfa doses based upon clinical judgment and presence/severity of prior infusion reactions. This regimen may be modified based on local treatment standards and guidelines as appropriate provided it does not include systemic corticosteroids.

In addition, immune-mediated side effects might be possible (immune-related pneumonitis, immune-related colitis, immune-related hepatitis, immune-related endocrinopathies (thyroid disorders, adrenal insufficiency, new onset type I diabetes mellitus, pituitary disorders), immune-related nephritis and renal dysfunction and other immune-related AEs (arthralgias, arthritis, myositis, myocarditis, Guillain-Barré syndrome, uveitis, thrombocytopenia, dry eyes, dry mouth, psoriasis, neuritis). Per IB, in the pooled expansion cohorts the incidence of all immune-related AEs was 21.7% (123 of 630 participants), with Grade 3 and 4 events being 8.5% (53 participants), 2.9% (18 participants) leading to discontinuation and 0.3% (2 participants) leading to death.

Please refer to the IB for detailed toxicity information.

14.1.3 Formulation and preparation

Bintrafusp alfa is provided as a sterile liquid formulation and packaged at a 10 mg/mL concentration in USP/ Ph Eur type I 50R vials that are filled with drug product solution to allow an extractable volume of 60 mL (600 mg/60 mL). The vials are closed with rubber stoppers in serum format complying with USP and Ph Eur with an aluminum crimp seal closure. Each single-use vial contains 600mg of bintrafusp alfa, formulated as 10mg/mL of active, 6% (w/v) Trehalose, 40 mM NaCl, 5 mM Methionine, 0.05% (w/v) Tween 20, 10 mM L-Histidine at pH 5.5.

The liquid formulation is diluted directly with 0.9% sodium chloride solution for injection. The estimated volumes of delivery are anticipated to be no more than 250mL. The verified concentration range in the infusion solution is 0.16 mg/mL to 9.6 mg/mL.

14.1.4 Stability and Storage

Bintrafusp alfa must be stored at 2°C to 8°C until use. Product stored at room temperature for extended periods of time might be subject to degradation. Bintrafusp alfa must not be frozen. Rough shaking of the reconstituted solution must be avoided.

The chemical and physical in-use stability for the infusion solution of bintrafusp alfa in 0.9% sodium chloride for injection has been demonstrated for a total of 72 hours at room temperature; however, from a microbiological point of view, the diluted solution should be used immediately and is not intended to be stored unless dilution has taken place in controlled and validated aseptic conditions. No other drugs should be added to the infusion containers containing bintrafusp alfa. See Manual of Preparation of approved ancillary supplies.

14.1.5 Administration procedures

See Section [3.3.3](#).

14.1.6 Incompatibilities

Not available.

16 LIST OF ABBREVIATIONS

Abbreviation	Term
AACR	American Association for Cancer Research
AAO-HNS	American Academy of Otolaryngology-Head and Neck Surgery
ACAT	Ability to Consent Assessment Team
ADA	anti-drug antibodies
ADR	adverse drug reactions
AE	Adverse Event/Adverse Experience
AESI	Adverse Event/Experience of Special Interest
AHNS	American Head and Neck Society
ALT	alanine transaminase
ANC	Absolute neutrophil count
ARS	American Rhinologic Society
ASCO	American Society of Clinical Oncology
AST	aspartate aminotransferase
BARON	Bintrafusp alfa in Recurrent/Metastatic Olfactory Neuroblastoma
β-HCG	Beta human growth hormone
BSI	Biospecimen Inventory System
BTRIS	Biomedical Translational Research Information System
CAP or C/A/P	Chest, abdomen, pelvis
CBC	Complete blood count
CCR	Center for Cancer Research
CD4	cluster of differentiation 4
CD8	cluster of differentiation 8
CFR	Code of Federal Regulations
CK	Creatine kinase
CLIA	Clinical Laboratory Improvement Amendment
CN	checkpoint-naïve
CNS	Central nervous system
CONSORT	Consolidated Standards of Reporting Trials
COV	Close-out Visit
CR	checkpoint-resistant
CR	Complete Response
CSP	Clinical Services Program
CRADA	Cooperative Research and Development Agreement
CRIS	Clinical Research Information System
CRF	Case Report Form
CT	Computed Tomography
ct DNA	Circulating tumor DNA
CTCAE	Common Terminology Criteria for Adverse Events
dbGaP	database of Genotypes and Phenotypes
DNA	Deoxyribonucleic acid

Abbreviation	Term
DO	Duration of Response
ECG / EKG	Electrocardiogram
ECOG	Eastern Cooperative Oncology Group
EDTA	Ethylenediaminetetraacetic acid
ELISA	enzyme-linked immunosorbent assay)
FDA	Food and Drug Administration
FDG	fluorodeoxyglucose
FFPE	Flash frozen, paraffin embedded
EOT	End of treatment
FT4	free thyroxine
GCP	Good Clinical Practice
GLP	Good Laboratory Practices
GMB	Genitourinary malignancies branch
GMP	Good Manufacturing Practices
GOT	Glutamic oxaloacetic transaminase
GPT	glutamate pyruvate transaminase
HBV	Hepatitis B virus
HCV	Hepatitis C virus
HHS	Health and Human Services
HIV	Human immunodeficiency virus
H&P	History and Pathology
IB	Investigator's Brochure
ICBMs	immune checkpoint blockade monoclonal antibodies
ICH	International Conference on Harmonisation
iCPD	confirmed progressive disease
IHC	Immunohistochemistry
IMV	Interim Monitoring Visit
IND	Investigational New Drug
INR	International Normalized Ratio
irAE	Immune-related adverse reactions
IRB	Institutional Review Board
IRBO	Institutional Review Board Office
iRECIST	immune Response Evaluation Criteria in Solid Tumors
IRR	Immune-related reaction
iUPD	unconfirmed progressive disease
IV	Intravenous
LAR	Legally Authorized Representative
LTIB	Laboratory of Tumor Immunology
MAR	Medical Administration Record
MDSC	myeloid-derived suppressor cell
MRI	Magnetic Resonance Imaging
MUGA	multi-gated acquisition scan

Abbreviation	Term
N	Number (typically refers to subjects)
NASBS	North America Skull Base Society
NCI	National Cancer Institute
NCI PDM	NCI Participant-Derived Models Repository
NCT	National Clinical Trial (number)
NFGCF	NCI Frederick Genomic Core Facility
NIDCD	National Institute of Deafness and Craniofacial Disorders
NIH	National Institutes of Health
NK	natural killer cells
NORD	National Organization for Rare Disorders
NSAID	Non-steroidal anti-inflammatory drugs
NSCLC	Non- small cell lung cancer
OHSRP	Office for Human Subjects Research Protections
ONB	Olfactory Neuroblastoma
ORR	objective response rate
OS	Overall survival
OSRO	Office of Sponsor and Regulatory Oversight
OTC	over the counter
PBMC	peripheral blood mononuclear cell
PCR	Polymerase Chain Reaction
PD	Progressive Disease
PD-1	programmed death 1
PD-L1	programmed death-ligand 1
PET	Positron Emission Tomography
PFS	Progression-free survival
PI	Principal Investigator
PK	pharmacokinetics
PR	Partial Response
PS	Performance Status
PT	Prothrombin time
PTT/aPTT	Partial Thromboplastin Time/activated Partial Thromboplastin Time
QA	Quality Assurance
QC	Quality Control
RECIST	Response Evaluation Criteria in Solid Tumors
RNA	Ribonucleic acid
SAE	Serious Adverse Event/Serious Adverse Experience
SAV	Site Assessment Visit
SIV	Site Initiation Visit
SEER	Surveillance Epidemiology and End Results
SD	Stable Disease
SLD	sum of the longest diameters

Abbreviation	Term
SOP	Standard Operating Procedure
SST	serum separation tubes
TBNK	T, B, and natural killer cells
TEAE	treatment-emergent adverse events
TGF- β	transforming growth factor beta
TGF- β RII	human TGF- β receptor II
TR	treatment-related
TRAIL	tumor necrosis factor-related apoptosis-inducing ligand
TSH	thyroid stimulating hormone
ULN	Upper limit of normal
US	United States
WBC	White blood cell
WOCBP	Women of child-bearing potential

17 APPENDICES

17.1 APPENDIX A: PERFORMANCE STATUS CRITERIA

ECOG Performance Status Scale		Karnofsky Performance Scale	
Grade	Descriptions	Percent	Description
0	Normal activity. Fully active, able to carry on all pre-disease performance without restriction.	100	Normal, no complaints, no evidence of disease.
		90	Able to carry on normal activity; minor signs or symptoms of disease.
1	Symptoms, but ambulatory. Restricted in physically strenuous activity, but ambulatory and able to carry out work of a light or sedentary nature (e.g., light housework, office work).	80	Normal activity with effort; some signs or symptoms of disease.
		70	Cares for self, unable to carry on normal activity or to do active work.
2	In bed <50% of the time. Ambulatory and capable of all self-care, but unable to carry out any work activities. Up and about more than 50% of waking hours.	60	Requires occasional assistance, but is able to care for most of his/her needs.
		50	Requires considerable assistance and frequent medical care.
3	In bed >50% of the time. Capable of only limited self-care, confined to bed or chair more than 50% of waking hours.	40	Disabled, requires special care and assistance.
		30	Severely disabled, hospitalization indicated. Death not imminent.
4	100% bedridden. Completely disabled. Cannot carry on any self-care. Totally confined to bed or chair.	20	Very sick, hospitalization indicated. Death not imminent.
		10	Moribund, fatal processes progressing rapidly.
5	Dead.	0	Dead.

17.2 APPENDIX B: RECOMMENDATIONS FOR MANAGEMENT OF IRRS AND AEs

TABLE A MANAGEMENT OF INFUSION-RELATED REACTIONS

NCI-CTCAE 5.0 Grade	Treatment Modification for Infused Agent (Bintrafusp alfa)
Grade 1 – mild Mild transient reaction; infusion interruption not indicated; intervention not indicated.	Consider decreasing the infusion rate of the particular agent by 50% and monitoring closely for any worsening.
Grade 2 – moderate Therapy or infusion interruption indicated but responds promptly to symptomatic treatment (e.g., antihistamines, NSAIDs, narcotics, i.v. fluids); prophylactic medications indicated for ≤ 24 hours.	Consider temporarily discontinuing infusion of the particular agent. Consider resuming infusion of the particular agent at 50% of previous rate once infusion related reaction has resolved or decreased to at least Grade 1 in severity and monitor closely for any worsening.
Grade 3 or Grade 4 – severe or life-threatening Grade 3: Prolonged (e.g., not rapidly responsive to symptomatic medication and/or brief interruption of infusion); hospitalization indicated for clinical sequelae. Grade 4: Life-threatening consequences; urgent intervention indicated.	Stop the infusion immediately and disconnect infusion tubing from the subject. For grade 3 events: Consider withdrawing immediately from treatment with that particular agent and not offering any further treatment with that agent based upon if the clinical condition can be safely managed. For grade 4 events: Withdraw immediately from treatment and do not offer further treatment with that agent.

If the infusion rate of bintrafusp alfa has been decreased by 50% or interrupted due to an infusion reaction, keep it decreased for the next scheduled infusion. If no infusion reaction is observed in the next scheduled infusion, the infusion rate may be returned to baseline at the subsequent infusions based on investigator's medical judgment.

If hypersensitivity reaction occurs, the subject should be treated according to the best available medical practice.

TABLE B Management of immune-related Adverse Events

Recommended guidance and management for specific irAEs as provided in the current NCCN guideline available at <http://www.nccn.org>.

According to American Society of Clinical Oncology Clinical Practice Guideline (Brahmer 2018), treatment of irAEs is mainly dependent upon severity as defined by NCI-CTCAE v5.0. In general, management by NCI-CTCAE v5.0 grading is listed below:

- Grade 1: study intervention should be continued with close monitoring, with the exception of some neurologic, hematologic, and cardiac toxicities.
- Grade 2: study intervention may be suspended for some Grade 2 toxicities, with consideration of resuming when symptoms revert to Grade 1 or less. Corticosteroids may be administered (initial dose of 0.5 to 1 mg/kg/day of prednisone or equivalent).
- Grade 3: study intervention is generally suspended and the high-dose corticosteroids (prednisone 1 to 2 mg/kg/day or methylprednisolone 1 to 2 mg/kg/day) treatment should be initiated. Corticosteroids should be tapered over the course of at least 4 to 6 weeks. Some refractory cases may require infliximab or other immunosuppressive therapy.
- Grade 4: in general, permanent discontinuation of study intervention is recommended, with the exception of endocrinopathies that have been controlled by hormone replacement.

Permanent treatment discontinuation is required in case of immune-related Grade 4 rash/inflammatory dermatitis, nephritis, autoimmune hemolytic anemia, hemolytic uremic syndrome, aplastic anemia, immune thrombocytopenia, and acquired thrombotic thrombocytopenic purpura.

For Grade 4 immune-related lymphopenia, permanent treatment discontinuation will be required, if lymphopenia is considered immune-related in nature, no clear alternative explanation exists for the event, and it does not resolve within 14 days. Permanent treatment discontinuation is not required when the AE is manifested by a single laboratory value out of normal range without any clinical correlates. In this case, treatment should be held until the etiology is determined. If the event is not considered immune-related and resolves to Grade ≤ 1 , restarting treatment may be considered.

For organ/system specific management guidelines, see the current NCCN guideline available at <http://www.nccn.org>.

TABLE C Management of TGF- β mediated Skin Adverse Events

Skin assessment must be performed at baseline and at least every 6 weeks during treatment and at the end of treatment or 28 (± 5 days) days post-treatment safety follow-up (if not performed in the previous 6 weeks).

- Hyperkeratosis
- Keratoacanthoma
- Cutaneous squamous cell carcinoma (cSCC)
- Basal cell carcinoma
- Actinic keratosis

Management

- Baseline skin assessment with detailed medical history
- Discontinuation or termination not required in most cases. Continuation of treatment should be evaluated by the Investigator.
- Emollients may be used
- Develop diagnostic and treatment plan in collaboration with Investigator and dermatologist
- Treatment follow-up will depend on number and localization of lesions.
 - Single lesion: full excision may be recommended
 - Multiple lesion or location not suitable for full excision: Mohrs surgery, cryotherapy or other standard treatment options depending on pathology. Topical retinoids may be used after discussion with Investigator.
- Close clinical follow-up for re-evaluation, resolution and potential recurrence should be implemented
- In general, treatment of TGF- β mediated skin lesions should be based on local guidelines/standard of care.

Additional consideration: Keratoacanthoma lesions may resolve spontaneously without surgical intervention within weeks after discontinuing bintrafusp alfa.

Consult with Medical Monitor as needed for management of TGF- β mediated skin lesions.

Management of Mucosal/Non-tumor and Tumor Bleeding

Mucosal Bleeding	

Events of mild to moderate severity are a potential risk for bintrafusp alfa.In general, these reactions resolve without discontinuation of treatment.Events may include, but are not limited to the following:
EpistaxisHemoptysisGingival bleedingHematuria	
Non-tumor Bleeding	
Grading	Management
Grade 2	
If resolves to Grade ≤ 1 by the day before the next infusion, study intervention may be continuedIf not resolved to Grade ≤ 1 by the day before the next infusion, but is manageable and /or not clinically relevant, consult Medical Monitor to assess if clinically reasonable to administer the following infusion.
Grade 3	
Permanently discontinue treatment unless an alternative explanation can be identified (such as concomitant use of antithrombotic agents, traumatic events, etc.)In case of alternative explanations, hold study treatment until the event recovers to Grade ≤ 1
Grade 4	
Treatment must be permanently discontinued if no alternative explanation is identified.
Tumor Bleeding	
Grade ≥ 2	
Study treatment must be held till the event recovers to Grade ≤ 1Permanently discontinue treatment if the Investigator considers the participant to be at risk for additional severe bleeding.

Guideline on Alterations in Wound Healing or Repair of Tissue Damage


Alterations of wound healing and tissue damage repair are considered an important risk for bintrafusp alfaManagement should be discussed with Medical Monitor for participants requiring surgery on study.It is recommended to hold study intervention for approximately 4 weeks post major surgery for observation.Post-operative wound healing should be closely monitored

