3.4 DOSE MODIFICATIONS

3.4.1 Discontinuation

Treatment with bintrafusp alfa will be discontinued in participants experiencing specific adverse events; subjects will remain on study for follow up of survival. Treatment will be discontinued in any participant in the case of:

- Any Grade 4 or higher adverse drug reactions (ADRs) graded according to NCI CTCAE v5.0 and assessed as possibly related to that agent by the Investigator, except for laboratory values that are asymptomatic or resolve to Grade ≤ 1 or baseline grade within 7 days without medical intervention.

- Any Grade 3 ADRs possibly attributed to any agent **except** for any of the following:
 - Transient (\leq 48 hours) Grade 3 nausea and vomiting, headache, flu-like symptoms, fever, controlled with appropriate medical management.
 - Tumor flare phenomenon defined as local pain, irritation, or rash localized at sites of known or suspected tumor.
 - Endocrinopathy that can be medically managed with hormone replacement.
 - Keratoacanthoma and squamous cell carcinoma of the skin. Suspicious skin lesions will be evaluated by dermatology and managed per recommendations (**Appendix B**: Recommendations for Management of IRRs and AEs, Table C), including potential removal of the lesion.
 - Grade 3 laboratory test abnormalities that resolve to Grade \leq 1 or to baseline Grade within 7 days with appropriate medical management or Grade 3 laboratory test abnormalities that are determined not to be clinically significant or asymptomatic.
 - Grade 3 anemia with Hgb <8.0 g/dL that is clinically manageable with PRBC transfusions does not require treatment discontinuation.
 - Any Grade 3 ADR which in the opinion of the investigator is not clinically relevant or can be managed with minimal risk to the participant (e.g. placement of a pleural catheter for recurrent inflammatory pleural effusions).

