3.4.2 Dose delay

- Bintrafusp alfa should be withheld for Grade \geq 2 epistaxis or any Grade \geq 2 toxicity possibly attributed to the study agent until resolution to Grade \leq 1 unless the toxicity in the opinion of the investigator is not clinically relevant or can be medically managed with minimal risk to the participant. Should a clinically relevant grade 2 or 3 toxicity persist for more than 4 weeks, consideration should be given to discontinuing treatment at the discretion of the investigator.
- Laboratory abnormalities which are clinically non-significant and/or unrelated to the agent in the judgement of the investigator, will not lead to dose delays.
- Grade 3 fatigue, headache, nausea, emesis that resolve to Grade \leq 1 with appropriate medical management will not lead to dose delays.
- Management recommendations for infusion-related adverse reactions are found in **Appendix B**: Recommendations for Management of IRRs and AEs, Table A Management of Infusion-related Reactions and should be followed along with institutional standards.
- Immune-related adverse reactions (irAE) should lead to treatment modifications and management per the summarized NCCN recommendations found in **Appendix B**: Recommendations for Management of IRRs and irAEs, Table B Management of immune-related adverse events. Investigators may refer to the relevant guidelines available by ASCO (62), SITC (63), NCCN (64), and ESMO (65).
- For non-medical logistical reasons, unrelated acute illnesses, or palliative radiation, scheduled assessments and dosing can be delayed up to 2 months. Following this interval treatment may resume, and where at all possible, dosing should be restarted to keep in line with the original treatment schedule.

- Local tumor flare phenomenon defined as local pain, irritation, or rash localized at sites of known or suspected lesions will not be considered adverse event or lead to dose interruptions.

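### The Section 3.4.1 investigator exemption can permit re-dosing after a related, unexplained Grade 3 non-tumor bleed, for which the Appendix B bleeding table requires permanent discontinuation

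*Combined protocol and SAP*

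**What the plan says.** Section 3.4.1 lists the events for which treatment will be discontinued.

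- At Grade 4 the entry is "Any Grade 4 or higher adverse drug reactions (ADRs) graded according to NCI CTCAE v5.0", if assessed as possibly related. The only exception is for certain laboratory values.
- At Grade 3, possibly attributed reactions also end treatment, subject to a list of exceptions. The last and broadest is "Any Grade 3 ADR which in the opinion of the investigator is not clinically relevant or can be managed with minimal risk". None of the exceptions mentions bleeding, either to include it or to exclude it.

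Sections 3.1.1 and 3.9.1 both refer to Section 3.4.1 for stopping treatment.

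Section 3.4.2 holds treatment for epistaxis, or any possibly attributed toxicity, of Grade 2 or higher until it falls to Grade 1 or less, "unless the toxicity in the opinion of the investigator is not clinically relevant or can be medically managed with minimal risk to the participant". It adds: "Should a clinically relevant grade 2 or 3 toxicity persist for more than 4 weeks, consideration should be given to discontinuing treatment". Section 3.4.4 allows reduced doses at the investigator's discretion and gives drug-caused hemorrhage of Grade 1 or higher as its example.

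The bleeding table in Appendix B separates non-tumor from tumor bleeding. For Grade 3 non-tumor bleeding the instruction is "Permanently discontinue treatment unless an alternative explanation can be identified". Where there is another explanation, treatment is held until recovery to Grade 1 or less. The tumor-bleeding row covers Grade 2 and above. It requires a hold until recovery, and a permanent stop if the investigator sees a risk of further severe bleeding.

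**The concern.** The Appendix B row for Grade 3 non-tumor bleeding turns on one question: is there another cause? Section 3.4.1 turns on a different one: does the investigator think the event unimportant or safely manageable? A bleed can have no other cause and still be judged manageable. In that case one text requires a permanent stop, while the section used as the stopping rule lets treatment go on.

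This matters for this drug and this tumor. Section 12.1 gives the drug's risk of severe bleeding as the reason participants must be willing to accept transfusion. Section 8.1.6 makes mucosal bleeding an adverse event of special interest. The tumor arises in the nasal cavity. An investigator working from Section 3.4 alone could re-dose a participant whom the appendix would take off treatment, and would meet no cross-reference giving notice of the other rule. The descriptive report of adverse events leading to discontinuation (Section 10.4.3) would also depend on which text was followed.

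**Working it through.** The plan states no figure on this point, so there is none to reproduce. The check compares the texts and counts the cross-references.

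**Step 1. The event.** Take a non-tumor bleed of Grade 3, possibly related to the drug, with no alternative explanation.

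| | Exemption not used | Exemption used |
|---|---|---|
| Section 3.4.1 | Discontinue | Treatment may continue |
| Appendix B bleeding table | Discontinue permanently | Discontinue permanently |
| Agreement | Yes | No |

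The divergence lies in one cell and comes from one exemption in Section 3.4.1.

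**Step 2. What follows once the exemption is used.** The participant is no longer caught by Section 3.4.1. Sections 3.4.2 (hold and resume) and 3.4.4 (dose reduction) then become available. They are consequences of the exemption and not separate sources of conflict.

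**Step 3. Does the text lead the reader to the bleeding table?** Pointers to Appendix B in the body of the protocol:

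1. Section 3.3.3: infusion rates after an infusion-related reaction.
2. Section 3.4.1: skin lesions, Table C ("Suspicious skin lesions will be evaluated by dermatology and managed per recommendations").
3. Section 3.4.2: "Table A Management of Infusion-related Reactions and should be followed along with institutional standards".
4. Section 3.4.2: "Table B Management of immune-related adverse events".

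Of these 4 pointers, 0 lead to the bleeding table, which carries no table letter.

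**Step 4. Is precedence stated?** No. Sections 3.1.1 and 3.9.1 cite Section 3.4.1, but neither says how it ranks against Appendix B. If a reader infers that Section 3.4.1 governs, the more lenient text prevails for this event.

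**Step 5. Can the frequency be bounded?** Not for this event. Section 14.1.2 tabulates related events that led to permanent discontinuation in at least 2 of 630 pooled participants, and no bleeding term appears. Each single bleeding term therefore accounted for at most 1/630 = 0.16%. If that carried over to the 32-participant accrual ceiling, it would be at most 32 × 1/630 = 0.05 participants per term. This is a bound per term, from other tumors and under other trials' stopping rules. It counts discontinuations and not Grade 3 bleeds. The same section reports one treatment-related death with intracranial tumor hemorrhage.

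**The case against.** The strongest reply is that the gap is narrow. Both texts discontinue by default, and they part only if the investigator judges an unexplained, related Grade 3 bleed unimportant or safely manageable. Many investigators would not. Some nasal bleeding will also count as tumor bleeding or have another explanation, since epistaxis is a presenting symptom of the disease (Section 1.2.1). Appendix B is titled as recommendations, so Section 3.4.1 may be meant to govern. Other safeguards exist: exclusion of recent clinically significant bleeding, roughly weekly team review, and a DSMB.

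The narrowness stands, and it limits the point. The title does not settle the matter, because the bleeding rows are worded as requirements and nothing marks them as advisory. The safeguards do not tell an investigator which rule to apply to the participant at hand.

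Three stronger readings are tempting, and the documents do not support them:

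- **Grade 4 tumor bleeding as a second outright conflict.** A reader might infer that the tumor-bleeding row allows treatment to resume after a related Grade 4 bleed. Section 3.4.1 is mandatory for such events, and the row never says treatment may restart after Grade 4. Discontinuing breaches nothing in the row. The mismatch is implied only, and one clause clears it up.
- **Section 3.4.4 as a separate permission to re-dose.** Its example has no upper grade. Read that way, it would also allow reduced dosing after Grade 4 and so contradict Section 3.4.1. It is better read as applying to participants not already discontinued.
- **Sizing by epistaxis.** Section 14.1.2 gives 12% for epistaxis of any grade. It does not give the share that was Grade 3, so the figure says nothing about how often this event occurs.

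**Conclusion.** The inconsistency is real and confined to one event: a possibly related Grade 3 non-tumor bleed with no alternative explanation, when the investigator uses the Section 3.4.1 exemption. For that event, following Section 3.4 can permit re-dosing that Appendix B forbids, and the missing cross-reference makes this easier to overlook.

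Its frequency is unknown, and the documents offer no usable estimate. The primary ORR analysis is unaffected. Beyond safety, only the descriptive reporting of discontinuations could change. The conclusion rests on reading the Appendix B bleeding rows as instructions, as they are worded. It should be corrected because it concerns participant safety on a named risk and the correction is small.

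**What to change.** 1. In Section 3.4.1, cite the Appendix B bleeding table. State that the Grade 3 investigator-discretion exemption does not apply to Grade 3 non-tumor bleeding without an alternative explanation, and that hold-and-resume under Section 3.4.2 and dose reduction under Section 3.4.4 are therefore not available for it.
2. As a secondary clarification, add to the Appendix B tumor-bleeding row that possibly related Grade 4 tumor bleeding means permanent discontinuation under Section 3.4.1.

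A general sentence that the stricter text always prevails is not advised. It would remove the Section 3.4.2 investigator exception for Grade 2 tumor bleeding, and would require the Medical Monitor to be consulted for every unresolved Grade 2 non-tumor bleed. Those are clinical trade-offs that go beyond this inconsistency.

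The cost is a protocol amendment, with no added visits or procedures, and possibly slightly more bleeding-related discontinuations.
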